- Is there any difference between the four repeated (at immediate, 4-week, 8-week, and 12-week follow-up) work engagement tests between the intervention and control group in terms of the mean?
- Is there any difference between the four repeated (at immediate, 4-week, 8-week, and 12-week follow-up) perceived professional benefit tests between the intervention and control group in terms of the mean?

3. Research Objectives

General objective:

Evaluate the impact of expressive writing (EW) intervention on stress and work-related outcomes among Chinese student nursing interns

Specific objectives:

- To compare the effectiveness of EW (expressive writing) and NW (neutral writing) in managing clinical practice stress among student nurse interns between intervention and control groups at immediate and 4-week, 8-week, and 12-week follow-up.
- To compare the impact of EW and NW on improving coping strategies among student nurse interns between intervention and control groups at immediate and 4-week, 8-week, and 12-week follow-up.
- To evaluate the effectiveness of EW and NW in promoting work engagement between intervention and control groups at immediate and 4-week, 8-week, 12-week follow-up.
- To compare the impact of EW and NW on promoting perceived professional benefit among student nurse interns between intervention and control groups among student nurse interns at immediate and 4-week, 8-week, and 12-week follow-up.

4. Study Design

A randomized controlled trial with parallel design.

5. Inclusion and Exclusion Criteria of Participants

Inclusion criteria:

- Undergraduate student nurse interns in their first clinical internship (had no prior clinical practice experience)
- Have access and proficiency in utilizing social media
- Be able to read and write via the internet
- Be willing to fill in questionnaires and write according to the assigned writing prompts
- Never participated in an expressive writing or stress management intervention programs

Exclusion criteria:

- Intern at a self-contacted hospital
- Severe current psychological conditions
- Undergoing any form of psychotherapy
- With a habit of keeping diaries

Withdrawal criteria:

- Termination of internship for whatever reason
- Not submitting writing materials twice

6. Sample Size

Using the sample size formula for comparing the means of two independent samples of continuous variables to calculate the sample size.

$$n_i = 2 \left(\frac{Z_{1-\alpha/2} + Z_{1-\beta}}{ES} \right)^2$$

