$$ES = \frac{|\mu_1 - \mu_2|}{\sigma}$$

To detect between-group differences with an effect size of 0.69 in clinical practice stress by Stress Rating Scale for Nursing Students in Practice after 10 weeks of intervention (primary outcome), with an α level of 0.05, we require 33 participants per group to attain a power of 80%. Accounting for an expected 10% loss to follow-up, we should include 74 participants.

7. Sampling and Grouping

All eligible student nurse interns in the four target hospitals constituted the sampling frame. Two of the four target hospitals will be selected by lottery and the intervention and control groups will be determined by a coin toss.

Participants will be sampled for both the intervention and control groups using the following method: all potential participants were entered alphabetically into Column A of the Excel sheet from A to Z. Then, random numbers will be generated in column B of the Excel sheet using the Rand() function. The 37 participants with small random numbers will be included as study participants in both groups.

A research assistant who will not be involved in other parts of the study completed all the above processes.

8. Blinding

This is a single-blinded randomized controlled study.

The intervention trainer will not be blinded, given that a single researcher conducts the study. To minimize experimenter bias, outcome assessments will be conducted through an online questionnaire survey platform (Wenjuanxing), with the trainer distributing the same link to all participants. During data

collection, only acronyms of the questionnaires will be used to avoid self-fulfilling expectations.

Participants will be informed during the recruitment phase only that the study aimed to explore the effect of writing on internship experience and feelings. Assignment to the intervention or control group will remain undisclosed to participants until the end of the 3-month follow-up.

Participants could unblind themselves by exiting the study and requesting debrief information.

9. Intervention Description

Intervention group:

According to the writing prompts, online expressive writing focuses on stressful events and will be conducted twice a week (every Monday and Thursday) for 15 minutes each time, lasting for ten weeks.

Writing prompts are developed based on Emotional Processing Theory (EPT) and Cognitive Adaptation Theory (CAT).

- 1st writing/Monday:

[figure not shown]

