- 2nd writing/Thursday:

Describe the specified object in the picture (from week one to week ten, provide pictures of the door, hairstyle, pants, room, hands, shoes, view from a window, clothes, water bottle, and computer).

In your writing, concentrate on the facts and details of the activity and thing you chose. We are not interested in your emotions or opinions, rather we want you to try to be completely objective. Feel free to be as detailed as possible.

To ensure the effectiveness of online writing, we developed a webpage suitable for the program. Participants can write from their computers or mobile devices. When a participant goes to the web page, the first page will be the instructions. This page shown before the writing tasks described the main objective of each task, emphasizing the importance of carefully reading the instructions. After reading the instructions, participants fill in their unique number and click on the "start writing" button. Then it will turn to the second

page for writing. There will be a countdown clock on this page, with the remaining time for the task. The clock flashed when one minute remained. When the time expires, the writing page will automatically close and display the final text. At this point, no editing was possible, but participants could read their texts.

10. Outcome Measures

All measures will be taken one day before the start of the intervention, one day after the end of the intervention, and followed up at 4 weeks, 8 weeks, and 12 weeks after the end of the intervention.

Primary outcome: Clinical Practice Stress

Stress Rating Scale for Nursing Students in Practice

The scale consists of 6 dimensions and 37 entries, including the nature of work, workload, preparation for an internship, interpersonal relationships, work support, and learning and work impulse. The scale rates on a 4-point Likert scale, with no stress, mild stress, moderate stress, and severe stress, assigned a score of 0, 1, 2, and 3, respectively, and the higher the score, the greater the stress.

Secondary outcome: Coping Strategy, Work Engagement, Perceived Professional Benefit

Brief Coping Style Scale

The scale consists of two dimensions, positive and negative coping, with 20 entries. A 4-point Likert scale is used, with 1-4 indicating "not used" to "often used". Positive coping has 12 entries, and negative coping has 8 entries, with higher scores indicating more frequent use of coping strategies.

Utrecht Work Engagement Scale

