The scale consists of 3 dimensions: vitality, dedication, and concentration, comprising 15 entries. A 7-point Likert scale is used, with scores ranging from 0-6 for "never," "almost never," "rarely," "sometimes," "often," "frequently," and "always." The total score is the sum of the scores of each entry. An average entry score of 4 or more is defined as a high level of work engagement, 2-4 as a moderate level, and less than 2 as a low level of work engagement.

Perceived Professional Benefits Scale

The scale consists of 7 items of positive career sense, 6 items of good nurse-patient relationship, 6 items of sense of belonging to the team, 8 items of self-growth, and 6 items of identification with friends and relatives, 33 items in 5 dimensions in total, and each item is scored 1 to 5 on a 5-point Likert scale ranging from "strongly disagree" to "strongly agree. The higher the score, the stronger the perceived professional benefit.

11. Data Analysis

Data will be analyzed with Stata version 14. All endpoints will be analyzed with generalized estimating equations and will use robust standard errors. The working correlation structure will be specified as exchangeable.

Data from all available time points will be used. The independent variables included in the model will be the treatment group (categorical) and the baseline value of the dependent variable (continuous). A model that additionally adjusted for age and sex for the primary endpoint will run.

The primary endpoint and secondary endpoints will all be analyzed with an intention-to-treat approach.

References

Ahmad, T. B., & Meltem Meriç, R. (2021). The effect of an online psychoeducational stress management program on international students'

ability to cope and adapt. *Perspectives in Psychiatric Care*, 57(4), 1673-1684. doi:10.1111/ppc.12735

Aloufi, M. A., Jarden, R. J., Gerdtz, M. F., & Kapp, S. (2021). Reducing stress, anxiety, and depression in undergraduate nursing students: Systematic review. *Nurse Education Today*, 102, 104877. doi:10.1016/j.nedt.2021.104877

Aslan, H., & Pekince, H. (2021). Nursing students' views on the COVID-19 pandemic and their perceived stress levels. *Perspectives in Psychiatric Care*, 57(2), 695-701. doi:10.1111/ppc.12597

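### The 80% power and 5% alpha in Section 6 assume independently allocated interns, but Section 7 puts one hospital in each arm, so both hold only if the hospitals do not differ

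*Protocol*

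**What the plan says.** - **Section 6 (Sample Size)** describes its method as "Using the sample size formula for comparing the means of two independent samples of continuous variables". With a standardised effect of 0.69 and alpha 0.05 it states "we require 33 participants per group to attain a power of 80" per cent, then raises the total to 74 for 10% loss. It mentions no ICC or design effect.
- **Section 7 (Sampling and Grouping)** says: "Two of the four target hospitals will be selected by lottery and the intervention and control groups will be determined by a coin toss". Candidates are then listed and given random numbers: "The 37 participants with small random numbers will be included as study participants in both groups".
- **Section 8 (Blinding)** adds: "Assignment to the intervention or control group will remain undisclosed to participants until the end of the 3-month follow-up".
- **Section 10 (Outcome Measures)** places the baseline measurement just before treatment: "All measures will be taken one day before the start of the intervention". Four measurements follow the intervention.
- **Section 11 (Data Analysis)** says: "All endpoints will be analyzed with generalized estimating equations and will use robust standard errors", with an exchangeable working correlation. On the model terms: "The independent variables included in the model will be the treatment group (categorical) and the baseline value of the dependent variable (continuous". One further model for the primary endpoint adds age and sex. Hospital appears in neither.

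**The concern.** The trial allocates hospitals but is sized and analysed as if it allocated interns. The coin-toss sentence does not name its unit. It does follow directly on the choice of two hospitals, and no later step assigns an individual to an arm. The random numbers select participants into groups that are already fixed, which is random sampling and not random allocation.

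With one hospital per arm, any difference between the two sites appears in full as a treatment difference. Such a difference is plausible for this outcome. The primary scale covers workload, interpersonal relationships and work support (Section 10), and the Introduction lists relations with clinical staff and an unfamiliar hospital environment among the stressors. If the sites differ at all, the planned p-values are too small and the confidence intervals too narrow, and a site difference could be reported as an effect of expressive writing.

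**Working it through.** **Inputs from the protocol.** Effect size 0.69, two-sided alpha 0.05, power 80%, 33 analysed per group, 10% loss, 37 recruited per group (Sections 6 and 7); two hospitals, one per arm (Section 7); baseline plus four post-intervention visits (Section 10).

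**Assumptions, because the protocol gives no values.** ICC between hospitals of 0.01, 0.02 or 0.05; within-person correlation of 0.6.

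**1. The plan's own figure.** n = 2 × ((1.960 + 0.842)/0.69)² = 32.97, so 33 per group. For dropout, 66/0.9 = 73.3, so 74. Both reproduce.

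**2. What needs no ICC.**
- One coin toss between two hospitals has 2 possible allocations. The smallest randomization p-value is 1/2 = 0.5 one-sided and 1.0 two-sided, so allocation alone cannot support a 0.05 claim.
- A design matrix with intercept, treatment and hospital has rank 2 for 3 columns. Adding a hospital term to the model is therefore no remedy.
- Clustering the GEE on intern omits between-hospital variance. Clustering on hospital leaves two clusters, one per arm, and 0 degrees of freedom.

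**3. Section 6 comparison, single visit, 33 per arm.**
- Design effect DEFF = 1 + 32 × ICC.
- Type I error = 2 × (1 − Φ(1.96/√DEFF)). If the naive standard error comes from within-hospital variance, DEFF is replaced by DEFF/(1 − ICC).
- Power, with the ICC treated as known = Φ(0.69 × √(33/(2 × DEFF)) − 1.96).

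| ICC | DEFF | Type I error | Power |
|---|---|---|---|
| 0.01 | 1.32 | 0.088–0.090 | 0.684 |
| 0.02 | 1.64 | 0.126–0.130 | 0.590 |
| 0.05 | 2.60 | 0.224–0.236 | 0.412 |

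Above an ICC of 1/32.97 = 0.030, no number of interns in two hospitals gives 80% power for this comparison.

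**4. Planned analysis, type I error.** Simulation under no treatment effect: 37 per arm, total variance 1, hospital variance equal to the ICC, correlation 0.6, no dropout, 20,000 replicates. Each data set was analysed as the baseline-adjusted mean of the four visits with an intern-level robust standard error. For complete balanced data this equals the exchangeable GEE.

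| ICC | Hospital effect also at baseline | Only after baseline |
|---|---|---|
| 0.01 | 0.077 | 0.184 |
| 0.02 | 0.102 | 0.285 |
| 0.05 | 0.163 | 0.461 |

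With no hospital effect the rate is 0.056–0.059, so a small part of the excess comes from the robust standard error and not from hospitals. At ICC 0.01, correlations of 0.4, 0.6 and 0.8 (10,000 replicates) give 0.098, 0.073 and 0.067 in the first scenario and 0.177, 0.183 and 0.240 in the second.

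**5. Planned analysis, power with the hospital variance known, 33 per arm.** The four-visit mean has within-hospital variance 0.6 + 0.4/4 = 0.70. After baseline adjustment this is 0.70 − 0.6² = 0.34, times (1 − ICC).
- Hospital effect only after baseline: variance of the difference = 2 × 0.34 × (1 − ICC)/33 + 2 × ICC. At ICC 0.01 this is 0.0204 + 0.02 = 0.0404, and power is Φ(0.69/√0.0404 − 1.96) = 0.93. At 0.02 and 0.05, power is 0.80 and 0.51.
- Hospital effect also at baseline: the last term becomes 2 × ICC × (1 − 0.6)². Power is at least 0.95 at all three ICCs.

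**6. Would all four target hospitals help?** With two per arm there are C(4,2) = 6 allocations, so the smallest two-sided randomization p-value is 2/6 = 0.33. A hospital-level t-test has 2 degrees of freedom. With the same 66 interns (16.5 per hospital, single visit), power is 0.352, 0.318, 0.291 and 0.234 at ICC 0, 0.01, 0.02 and 0.05.

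**The case against.** The strongest counter-argument concerns power. Section 11 plans a baseline-adjusted analysis of four visits, which is more efficient than the single-visit comparison in Section 6. Step 5 shows that it can keep 80% power or more at an ICC of 0.01 to 0.02. This stands: a fall below 80% in the planned analysis at those ICCs is not claimed, and the 68%, 59% and 41% belong to the Section 6 calculation only. It does not rescue the stated claim. Power of 80% at alpha 0.05 is a joint statement, and it fails once alpha is not held. The step 5 figures also need the hospital variance to be known, which one hospital per arm cannot provide.

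Second, every percentage rests on an assumed ICC and correlation, and on whether a hospital effect already exists at baseline. That is so. The size is a range; the direction is the same for any hospital variance left after baseline adjustment, and the aliasing needs no assumption.

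Third, the unit of the coin toss is inferred. An individual toss would fit poorly with exactly 37 interns sampled for each group, so this carries little weight, although Section 7 should name the unit.

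Fourth, the GEE clustering unit may properly be left to a statistical analysis plan. Its absence is not counted as a fault here; the point is that neither choice would work.

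**Conclusion.** The concern holds and must be fixed. Section 6 computes correctly from an assumption that Section 7 contradicts. As designed, an effect of expressive writing cannot be told apart from a difference between two hospitals, and no later analysis plan can change that.

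The stated alpha and power hold only at zero between-hospital variance. At an assumed ICC of 0.01 to 0.05, type I error is about 9% to 24% for the single-visit comparison. For the planned analysis at correlation 0.6 it is about 8% to 16% when the hospital effect is also present at baseline, and 18% to 46% when it arises afterwards. The conclusion depends on reading the coin toss as applying to hospitals; the percentages also depend on the assumed ICC and correlation.

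**What to change.** **If hospital allocation is kept.** Delete the 80% power and alpha 0.05 claims from Section 6. If the calculation stays as background to the figure of 74, label it as conditional on zero between-hospital variance. Name the hospital as the unit of allocation in Section 7. State in Section 11 that the confidence intervals and p-values exclude between-hospital variation and that the treatment effect cannot be separated from the hospital effect. The cost is wording only: no extra participants, but a less favourable statement of what the trial can show. The confounding is disclosed, not removed.

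**Alternative, only if allocation has not yet taken place.** Randomize interns individually within the two hospitals, stratified by hospital, and put hospital in the model. The calculation of 33 per group then applies. This changes an ethics-approved allocation and needs an amendment. It also brings a risk of contamination and unblinding, because both sets of prompts would run in one hospital while Section 8 requires assignment to stay undisclosed. Section 7 mixes tenses and describes the allocation steps partly as already done, so the sponsor should first confirm that this route is still open.

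Using all four target hospitals, two per arm, would not restore the claim (step 6 of the working).

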Research Proposal

Research title:

Effects of Expressive Writing on Stress and Work-Related Outcomes among Student Nurse Interns: a randomized controlled trial

NCT ID:

Not yet assigned

Date of the document:

[figure not shown]
October 17th, 2023

Research title:

Effects of Expressive Writing on Stress and Work-Related Outcomes among Student Nurse Interns: a randomized controlled trial

Funding sources:

Supported by the Program for the Philosophy and Social Sciences Research (PSSR) of Higher Learning Institutions of Shanxi, China (Project No.: 2023W103)

Research schedule:**Ethical Review:**

The Ethics Committee of Changzhi Medical College approved the study protocol on October 17, 2013, registration number RT2023047.

1. Introduction

Nursing internships are essential to nursing programs and a crucial stage in the early careers of nursing students. Those seeking hands-on experience in hospitals or medical facilities are known as student nurse interns. The clinical learning experience is considered a significant source of stress. The

stress level of nursing students during clinical practicum ranges from moderate to severe, affecting 47.82 to 100% of participants.

Stressors in the clinical setting included discrepancy between theory and practice, feeling unprepared, fear of making a mistake, issues related to death and dying, witnessing suffering, challenging interpersonal relationships with clinical staff, being observed and evaluated, communication with physicians, conflict between personal life and internship tasks, and unfamiliarity with the hospital environment. The rapid evolution of healthcare brings new stressors for nurses and nursing students. Health professionals often play down or deny mental health problems, which exacerbates the problem.

Stress not only affects the well-being of student nurse interns but also impacts job satisfaction and can lead to turnover in nursing. The stress of student nurse interns can affect motivation, communication, learning, clinical practice, and academic performance, which can be detrimental to patients. The American College Health Association (ACHA) and the Chinese Ministry of Education have taken steps to promote student mental health. Academic institutions actively conduct mental health research to develop effective strategies and programs.

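### Section 7 appears to give one whole hospital to each arm by a coin toss, so hospital and treatment cannot be separated

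*Protocol*

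**What the plan says.** Section 4 describes the study as "A randomized controlled trial with parallel design". Section 7 starts from the eligible interns in four hospitals and says: "Two of the four target hospitals will be selected by lottery and the intervention and control groups will be determined by a coin toss". The next paragraph of Section 7 samples interns for groups it already calls intervention and control. Names are listed alphabetically in a spreadsheet, each gets a random number, and "The 37 participants with small random numbers will be included as study participants in both groups". No sentence assigns an individual intern to expressive or neutral writing.

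Section 6 uses the standard formula for two independent means and concludes that "we require 33 participants per group to attain a power of 80" per cent, at a standardized effect of 0.69 and alpha 0.05. After 10% loss the total is 74. Section 11 plans generalized estimating equations (GEE) with robust standard errors: "The independent variables included in the model will be the treatment group (categorical) and the baseline value of the dependent variable (continuous"). One further model for the primary endpoint adds age and sex. Hospital appears in neither model.

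**The concern.** Two hospitals, two groups and one coin toss stand in a single sentence, and the random numbers come afterwards, as a sampling device. Read this way, the hospital is the unit of allocation and each arm has one unit. Everything that differs between the two hospitals then differs between the arms.

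That matters for this outcome. The primary stress scale covers several dimensions, "including the nature of work, workload, preparation for an internship, interpersonal relationships, work support, and learning and work impulse", and the Introduction counts "challenging interpersonal relationships with clinical staff" among the stressors. Staffing, supervision and workload plausibly belong to the hospital, and they can shift during the ten weeks of writing and twelve weeks of follow-up. Adjustment for a value taken one day before the intervention cannot remove what happens later.

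At stake is the general objective in Section 3: whether a difference between the groups can be attributed to expressive writing at all.

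**Working it through.** **1. The plan's own figure.** Inputs from Section 6: effect size 0.69, two-sided alpha 0.05, power 80%.

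- n per group = 2 × ((1.96 + 0.842)/0.69)² = 32.97, so 33.
- After 10% loss: 33/0.9 = 36.7, so 37 per group and 74 in total.

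The figure reproduces, but the formula holds only if interns are independent.

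**2. What the design fixes, without assumptions.** With one hospital per arm, the hospital column equals the arm column. A model with intercept, arm and hospital has rank 2 for 3 columns, so hospital cannot be added. A hospital-level comparison has 2 − 2 = 0 degrees of freedom. Robust standard errors clustered on interns do not see between-hospital variance, and clustering on hospital leaves only two clusters.

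**3. Illustration before baseline adjustment.** The protocol gives no ICC, so 0 to 0.10 is assumed, with m = 33 per hospital and a single follow-up.

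- SD of the chance difference between two hospitals = √(2 × ICC), in outcome SDs.
- True variance over the variance the analysis assumes = 1 + m × ICC/(1 − ICC).
- Type I error = 2 × (1 − Φ(1.96/√ratio)).

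| ICC | SD of hospital difference | Ratio | Type I error |
|---|---|---|---|
| 0 | 0 | 1 | 5.0% |
| 0.01 | 0.14 | 1.333 | 9.0% |
| 0.05 | 0.32 | 2.737 | 23.6% |
| 0.10 | 0.45 | 4.667 | 36.4% |

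The target effect is 0.69.

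**4. With baseline adjustment, as Section 11 plans.** Further assumptions: within-hospital baseline slope b = 0.6, and hospital effects correlated r between baseline and follow-up. Let k = 1 + b² − 2br, which is 0.76, 0.40 and 0.16 at r = 0.5, 0.8 and 1.0.

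- SD of the remaining hospital difference = √(2 × ICC × k).
- Ratio = 1 + m × ICC × k/((1 − ICC)(1 − b²)).
- Example at ICC 0.05, r = 0.5: 1 + 33 × 0.05 × 0.76/(0.95 × 0.64) = 3.06, which gives 26.3%.

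| ICC | r = 0.5 | r = 0.8 | r = 1.0 |
|---|---|---|---|
| 0.01 | 9.7% | 7.5% | 6.0% |
| 0.05 | 26.3% | 17.5% | 10.2% |
| 0.10 | 39.7% | 28.0% | 15.7% |

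At ICC 0.05 the remaining SDs are 0.276, 0.200 and 0.126. Even perfectly stable hospital effects are not fully removed, because a slope of 0.6 leaves 0.4 of the hospital difference (0.4 × 0.316 = 0.126).

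Simulation of the single-follow-up analysis of covariance (6,000 runs each) at ICC 0.05 gave 25.1%, 16.7% and 9.8%.

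**5. Four follow-ups.** The planned GEE pools four visits. Two checks at ICC 0.05:

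- Unadjusted four-visit mean, within-person correlation assumed 0.5, m = 33. Person variance = 0.95 × (1 + 3 × 0.5)/4 = 0.594. Hospital variance = 0.0125 if hospital effects are unrelated across visits, or 0.05 if constant. Ratios are 1.69 and 3.78; type I error is 13% and 31%.
- Simulated GEE with baseline, 37 per arm, and a hospital effect that is absent at baseline and then constant (600 runs): 41%.

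**6. The alternative.** Randomization within hospital with a hospital fixed effect (r = 0.8, single follow-up, 6,000 runs each) gave type I error of 5.5%, 4.7% and 5.2% at ICC 0.01, 0.05 and 0.10.

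**The case against.** The strongest objection is that one hospital per arm is inferred. Section 7 does not say what the coin is tossed for, it describes one spreadsheet and not one per hospital, and Sections 4 and 6 treat the study as an individually randomized trial. This stands as a limit on certainty, but it does not save the text. A toss for each intern would not reliably give two groups of exactly 37, and taking the 37 smallest numbers from a pooled list fills one group and leaves the other undefined. On every reading an individual allocation step is missing.

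It is also fair that the error rates are illustrations. ICC, slope and hospital-effect correlation are all assumed; at ICC 0 there is no inflation; the unadjusted rates describe an analysis that nobody plans; and most of the figures use one follow-up where the plan uses four. The true rate could lie above or below them. The complete confounding depends on none of this.

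Finally, all four hospitals could be used, two per arm, which keeps the prompts physically apart. That would end the complete confounding, but with 4 − 2 = 2 degrees of freedom between hospitals the comparison would remain weak.

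**Conclusion.** The concern holds and must be fixed. As most naturally read, Section 7 makes this a cluster-randomized comparison with one cluster per arm. Neither the model in Section 11 nor any later analysis plan can then tell a hospital effect from an effect of expressive writing, and the stated alpha and power do not hold as a test of the intervention.

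The 0 degrees of freedom follow from the design alone. The size of the error does not: about 6% to 40% after baseline adjustment, for ICC 0.01 to 0.10, slope 0.6 and hospital-effect correlation 0.5 to 1.0, and 5% at ICC 0. Baseline adjustment lessens the problem when hospital effects are stable but does not remove it. If individual allocation was intended, the defect is one of text, and Section 7 still has to be corrected.

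**What to change.** **Preferred change.**

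- Section 7: after consent and baseline, the independent research assistant randomizes individual interns to expressive or neutral writing within each hospital. With 37 sampled per hospital, allocate 19:18 in one and 18:19 in the other, so that each arm still has 37.
- Section 11: add hospital as a fixed effect.
- Section 9: the writing page shows instructions before the participant is identified ("After reading the instructions, participants fill in their unique number"). Use arm-specific links or ask for the number first, and ask interns not to share prompts.

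If individual allocation was always intended, Section 7 should say so.

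**Cost.** No extra participants. The hospital term takes 1 degree of freedom; two-sample t-test power at 33 per group is 78.8% with 64 or 63 degrees of freedom. The real price is contamination. Interns in one hospital may compare prompts, which could dilute the effect or reveal the assignment that Section 8 keeps undisclosed, and so bias self-reported outcomes in either direction. The request not to share may itself hint that prompts differ, so its wording needs care.

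**If hospital-level allocation must stay or has already been done.** Section 7 mixes past and future tense, so this is possible, and re-randomizing would then be more than a wording change. In that case describe the study as a two-hospital comparison with one cluster per arm, withdraw the power claim as a test of the intervention, and do not attribute differences causally to expressive writing.
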